#### 7.2.1. Inclusion Criteria

A participant must meet the following criteria to be eligible for inclusion in the study:

1. Is  $\geq 12$  years of age at randomization

*Note: participants  $<18$  years of age will only be enrolled where permitted by local requirements.*

2. Meets  $\geq 1$  of the following criteria:

- a. Solid organ transplant (SOT) or hematopoietic stem cell transplant (HSCT) recipients receiving immunosuppressive medication
- b. Active hematologic malignancies
- c. Solid organ malignancies receiving active treatment with T cell or B cell immunosuppressive therapy
- d. Primary immunodeficiency (such as hypogammaglobulinemia, common variable immune deficiency, severe combined immunodeficiency)
- e. HIV and CD4  $<200$  cells/microliter
- f. Patients with rheumatologic disease, autoimmune disease, or multiple sclerosis receiving immunosuppressive therapy that modulates Th1, Th17, anti-TNF such as infliximab, adalimumab, etanercept, or B cell responses
- g. Currently receiving any of the following immunosuppressant drugs:
  - T cell suppressing agents (eg,  $\geq 5$  mg prednisone equivalent/day during  $>3$  weeks)
  - Proteasome inhibitors (such as bortezomib, lenalidomide), alemtuzumab, anti-thymocyte globulin, CAR-T therapy, calcineurin inhibitors)
  - Alkylating agents and anthracyclines
  - Antimetabolites and purine analogues, such as mycophenolate, fludarabine, or cladribine
  - B cell targeted therapies, such as rituximab, ocrelizumab, CD19/CD20, and BTK inhibitors
  - mTOR inhibitors

- JAK/STAT pathway inhibitors

3. Has received a full course of standard-of-care COVID-19 vaccination per regional guidance, **or** is deemed medically ineligible or contraindicated to receiving a full course of standard-of-care COVID-19 vaccine
4. Has a documented negative (based on test reference values) serology/antibody response in an anti-SARS-CoV-2 spike (S) protein IgG clinical test (including, but not limited to, RBD-specific tests), **or** ≤50 U/mL on the Elecsys® SARS-CoV-2 S Total Ig test. The test should be performed on a sample collected at least 2 weeks after the final dose of a COVID-19 vaccine and within 3 months prior to randomization

*Note: Lateral flow immunoassay (LFIAs) results will not be accepted. Test should be considered acceptable for clinical use by local standards (approved or with EUA issued by the US FDA or by equivalent local health authority).*

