### 7.2.2. Exclusion Criteria

A participant who meets any of the following criteria will be excluded from the study:

1. Has a life expectancy of less than 2 years
2. Weighs <40 kg (only applies to participants ≥12 to <18 years of age)
3. Has any signs or symptoms consistent with COVID-19 (as determined by the investigator)
4. Has a history of SARS-CoV-2 infection within 90 days prior to randomization
5. Planned use of any investigational, authorized, or approved vaccine for COVID-19 within 90 days (or per current CDC recommendations) of the last dose of study drug ([CDC, 2021](#))
6. Prior, current, or planned use of any of the following treatments: COVID-19 convalescent plasma, other monoclonal antibodies against SARS-CoV-2 (eg, bamlanivimab and

etesevimab, sotrovimab), or any COVID-19 treatment (authorized, approved, or investigational)

*Note: Prior use is defined as the past 30 days or within 5 half-lives of the investigational product (whichever is longer) from screening.*

7. Is planned to begin intravenous immunoglobulin (IVIG) or subcutaneous immunoglobulin (SCIG) therapy, is planned to have a change to existing IVIG or SCIG regimen, or has been on a chronic stable dose of their IVIG or SCIG regimen for less than 90 days prior to screening.
8. Has any known active acute respiratory infection
9. Has no documented laboratory blood chemistry and hematology (including differential) results in the 6 months prior to randomization
10. Has persistent (refractory to treatment for  $\geq 14$  days) bacterial or fungal infection
11. Has known allergy or hypersensitivity to components of the study drugs
12. Has been discharged, or is planned to be discharged, to a quarantine center
13. Is a member of the clinical site study team or their immediate family member

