4.4.2. Post-Infection treatment

The following investigational dose levels will be offered as part of the study, and may be provided if medically indicated in the investigator's judgement:

- Not hospitalized due to COVID-19 and does not require supplemental oxygen or an increase in baseline oxygen flow rate due to COVID-19: **1200 mg** (600 mg per mAb), administered either intravenously or subcutaneously
- Hospitalized due to COVID-19 and does not require supplemental oxygen due to COVID-19, or requires low-flow supplemental oxygen due to COVID-19: **2400 mg** (1200 mg per mAb), administered intravenously
- Hospitalized due to COVID-19 and requires either high-intensity supplemental oxygen due to COVID-19 or requires mechanical ventilation due to COVID-19: **8000 mg** (4000 mg per mAb), administered intravenously

Administration of post-infection treatment with casirivimab+imdevimab will not require unblinding of the participant's randomization assignment.

Participants with a positive SARS-CoV-2 RT-PCR (from either local or central testing) will discontinue the study drug assigned at randomization and enter the follow-up period. This includes any participant for whom post-infection treatment with casirivimab+imdevimab was offered but was declined by the participant or investigator, or otherwise not received.

All participants with a positive SARS-CoV-2 RT-PCR will have **additional** assessments and sample collections, as noted in the Schedule of Events and summarized below):

- NP swab samples will be collected during unscheduled visits every 7 days (± 1 day) for central laboratory RT-qPCR analysis until 2 consecutive negative test results are obtained. During these visits, COVID-19 signs and symptoms will also be evaluated by the investigator or designee.
- Information regarding COVID-19-related medically-attended visits (MAVs) will be recorded, and participants will be asked to notify study personnel as soon as possible about such occurrences.

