4.5. Efficacy Variable

4.5.1. Primary Efficacy Variable

Primary efficacy variable is cumulative incidence of symptomatic (broad term), RT-PCR-confirmed SARS-CoV-2 infection cases during the efficacy assessment period (EAP). The conditions for symptomatic SARS-CoV-2 infection are as follows:

- At least 1 sign or symptom (broad term definition) confirmed by a study clinician (investigator or designee) to be related to COVID-19, **and**
- A positive SARS-CoV-2 RT-PCR result (local or central analysis), **with**
- The sign/symptom onset date and the date of collection for the positive sample occurring within ± 7 days of one another

The primary endpoint will analyze symptomatic SARS-CoV-2 infection during the efficacy assessment period (EAP). The EAP is defined as the day 2 to day 169 +7 days . In addition, following rules will be applied to the primary analyses:

- Time to first symptomatic infection is defined as the first date of having either central or local lab determined positive test result.
- Subjects do not experience any symptomatic infection will be censored at last observed time point.
- Subjects who die at any time in the study or discontinue the study earlier (did not get any infections) will be censored at the end of study in case of final database lock.
- Subjects with COVID-19 symptoms that are missing a central lab determined RT-qPCR test during the EAP but have a positive SARS-CoV-2 test from a local lab will be considered as having a symptomatic infection if any of the symptoms occurred within 7 days of the positive SARS-CoV-2 test that was observed during the EAP.
- If subjects took optional dose of 1200mg, all the data after the dose will be removed from the efficacy analyses.

If subjects took investigational, authorized, or approved COVID-19 vaccines within 90 days of the last dose of study drug (or per current CDC recommendations) (CDC, 2021) or any covid-19 treatment medications for prevention after starting study treatment (Anti SARS-CoV-2 antibodies including Bamlanivimab/ Etesevimab, Casirivimab/ Imdevimab (REGEN-COV), Sotrovimab or Tixagevimab/ Cilgavimab (Evusheld); remdesivir; Nirmatrelvir/ Ritonavir (Paxlovid); Molnupiravir, all the efficacy data after these treatment will be removed from efficacy analyses.

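### SAP 4.5.1's vaccine cut-off is not limited to vaccines given after day 1, so as written it can delete eligible, recently vaccinated participants, and tends to delete cases at least as often as comparable non-cases

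*SAP*

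**What the plan says.** The last rule in SAP 4.5.1 has two triggers, each with its own time qualifier. For vaccines it reads "If subjects took investigational, authorized, or approved COVID-19 vaccines within 90 days of the last dose of study drug", followed by a parenthesis allowing current CDC recommendations as an alternative, so the window itself is not fully fixed. For medications it reads "any covid-19 treatment medications for prevention after starting study treatment". The consequence is the same for both: "all the efficacy data after these treatment will be removed from efficacy analyses". SAP 4.5.2 carries similar rules to two exploratory incidence variables: symptomatic infection in the follow-up period, and infection regardless of symptoms.

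Three other provisions bear on how the vaccine trigger works:

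- Protocol 7.2.1, criterion 3: "Has received a full course of standard-of-care COVID-19 vaccination per regional guidance", unless the participant is medically ineligible or the vaccine is contraindicated. Criterion 4 requires the antibody test to come from a "sample collected at least 2 weeks after the final dose of a COVID-19 vaccine and within 3 months prior to randomization".
- Protocol 7.2.2, exclusion 5, looks only forward: "Planned use of any investigational, authorized, or approved vaccine for COVID-19 within 90 days" of the last dose. Past vaccination is not excluded.
- SAP 4.4.2 (and protocol 6.4.5): participants with a positive RT-PCR "will discontinue the study drug assigned at randomization and enter the follow-up period".

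**The concern.** The vaccine trigger is measured from the last dose, in either direction. A vaccine that qualified someone for entry can therefore lie within 90 days of that person's last dose if dosing ended early. Removing everything after such a vaccine removes every on-study efficacy record.

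The trigger also depends on the outcome. Infection ends assigned dosing and fixes the last dose early. An uninfected participant who keeps dosing moves out of reach of the rule. Cases can then be dropped more often than non-cases, and the Kaplan-Meier incidence is too low. With about 16 to 17 participants per arm, losing eligible participants, and any case among them, also matters in its own right.

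**Working it through.** **Inputs from the documents.** Injections are every 4 weeks in all arms (protocol 8.1), nominally on days 1, 29, 57, 85, 113 and 141. Day 1 is the first dose (SAP 6.4). Cases count from day 2 to day 176 (SAP 5.7.1). The 6-month placebo incidence is 4.02% (protocol Table 6). The documents give no figure for the vaccine rule, so there is none to reproduce.

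**Reach of the rule.** A vaccine given v days before day 1 is caught if v + (last-dose day − 1) ≤ 90.

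- Last dose day 1: v ≤ 90
- Last dose day 29: v ≤ 90 − 28 = 62
- Last dose day 57: v ≤ 90 − 56 = 34
- Last dose day 85: v ≤ 90 − 84 = 6, which is below the minimum gap of about 14 days, so nobody is caught

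With a 14-day minimum gap, the last dose must fall by day 90 − 14 + 1 = 77. A participant who completes dosing is never caught.

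**Worked records, final vaccine 40 days before day 1.** A case infected on day 20 has last dose day 1: 40 + 0 = 40, deleted. A non-case with last dose day 85: 40 + 84 = 124, kept. A non-case with last dose day 57: 40 + 56 = 96, kept. A non-case with last dose day 29: 40 + 28 = 68, also deleted.

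**Illustrative size.** Assume v is uniform on 15 to 180 days (166 values) and infection is uniform until 28 days after the last planned dose. The caught shares are 76/166 = 45.8%, 48/166 = 28.9% and 20/166 = 12.0% for last dose day 1, 29 and 57. Cases spread equally over the 28-day dosing blocks. Observed incidence is p(1 − c) / [p(1 − c) + (1 − p)(1 − n)], with p = 0.0402 and c, n the deleted shares of cases and non-cases.

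| Last planned dose | Non-cases deleted | Cases deleted | Observed incidence | Change |
|---|---|---|---|---|
| Day 29 | 28.9% | (45.8 + 28.9)/2 = 37.3% | 3.56% | −11% |
| Day 57 | 12.0% | (45.8 + 28.9 + 12.0)/3 = 28.9% | 3.27% | −19% |
| Day 85 | 0% | (45.8 + 28.9 + 12.0 + 0)/4 = 21.7% | 3.18% | −21% |

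With an upper limit of 240 or 120 days instead of 180, the fall ranges from 8% to 33%.

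**Early closure.** A simulated truncated trial assumed a 60- or 90-day entry window, assigned dosing ending 0, 30 or 60 days after enrollment closed, and gaps uniform on 14 to 90 or 14 to 180 days. It deletes 16% to 82% of cases, 4% to 79% of non-cases without the optional dose, and 0% to 44% of non-cases whose optional dose counts as the last dose. Within each scenario cases exceeded non-cases. If instead cases occur only after enrollment closes and dosing stops at closure, the rates are equal (36.7% and 36.7% with a 60-day entry window and gaps of 14 to 180 days).

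**Hazard ratio.** At any time, deletion multiplies each arm's hazard by (1 − share of cases deleted) / (1 − share of those at risk deleted). Allocation is randomized and blinded and infections are few, so this factor is essentially the same in every arm and cancels in the ratio. Simulation at the design rates, over the same vaccination limits and last-dose days, agrees. Arm 1 gives 0.396 to 0.402 before deletion and 0.397 to 0.402 after; arm 3 gives 0.545 to 0.553 before and 0.544 to 0.555 after.

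**Scale.** With 66/4 = 16.5 per arm, the design rates over full follow-up give 16.5 × (0.01628 + 0.01829 + 0.02231 + 0.0402) = 1.6 expected cases, of which 16.5 × 0.0402 = 0.66 are on placebo.

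**The case against.** The context points firmly to on-study vaccines. The clause repeats SAP 4.4.1, which concerns medication prohibited during the study. Protocol 8.9 defines concomitant treatment as given from the first dose onward, or started earlier and still ongoing. Exclusion 5 uses the same 90-day window prospectively. Protocol 8.3.2.1 stops dosing for a vaccine received during the study. A backward reading would make the vaccination required for entry a prohibited medication for some participants. One can also read the limiter on the medication trigger as governing both. This stands as evidence of intent. It does not correct the rule that has to be programmed, and protocol 8.3.2.1 shows that clear wording was available.

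Early closure narrows the contrast, because non-cases also stopped dosing early, and in the limit it disappears. The optional dose complicates it further. Protocol 9.1.2 treats that dose as the final dose for timing the last visit, but the SAP does not say whether it counts here. If a case without post-infection treatment later took it and it counted, the difference could shrink or reverse. Both points stand.

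The consequence is limited. SAP section 1 calls all endpoints exploratory, and p-values are nominal. A fall of 11% to 21% in 0.66 expected placebo cases is 0.07 to 0.14 of a case.

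A reader might infer that outcome-dependent deletion also biases antibody efficacy. The documents do not support this: the trigger does not use treatment arm, and the hazard ratio is unchanged in the calculation. Bias would need infection timing to differ by arm, which nothing here establishes.

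**Conclusion.** The point holds as a defect in the written rule. Applied literally, SAP 4.5.1 deletes all on-study efficacy data of eligible participants whose pre-study vaccine falls within 90 days of an early last dose. It does not delete every recently vaccinated participant: the last dose must fall by about day 77, in practice on day 1, 29 or 57.

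Cases tend to be deleted at least as often as comparable non-cases, with equality if all dosing stopped before any case occurred. The result is a downward bias in Kaplan-Meier incidence and a loss of scarce cases. Hazard ratios lose precision only, provided infection timing is similar across arms.

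The roughly 8% to 33% fall in incidence is illustrative. It rests on assumed uniform vaccination intervals, an assumed end of dosing, and no optional dose counted as the last dose; the documents give neither the intervals nor the dosing-stop dates. Given the probable intent and the descriptive analysis of 66 participants, this is a wording repair that should be made, not a threat to the trial's conclusions.

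**What to change.** Replace the vaccine part of the last rule in SAP 4.5.1 with: *If a participant receives any COVID-19 vaccine on or after day 1 (after the first dose of study drug), efficacy data are censored at the date of that vaccine.* The last-dose anchor should no longer decide whose data are removed.

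Adding a day-1 floor alone would stop the deletion of pre-study vaccinees but leave a gap in the other direction. With a last dose on day 1, a vaccine on day 100 is 99 days later and would not trigger the cut, although cases count to day 176. Dropping the anchor also makes it unnecessary to decide whether the optional dose is the last dose for this rule.

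The prohibited-medication text in SAP 4.4.1 and protocol 8.9.1 stays unchanged. With this wording, vaccination before day 1 deletes no cases and no non-cases in any of the scenarios above. The cost is one SAP sentence and one programming condition, with no extra data. If the analysis has already been run, the report should state which reading was programmed and how many participants it removed.

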4.5.2. Other Efficacy Variable(s)

The exploratory efficacy variables are:

1. Cumulative incidence of symptomatic (broad term), RT-PCR-confirmed SARS-CoV-2 infection cases during the follow-up period is defined as time to first symptomatic infection (RT-PCR-confirmed SARS-CoV-2) during the follow-up period. Similar rules to primary efficacy variable are applied to this variable.
2. Cumulative incidence of RT-PCR-confirmed SARS-CoV-2 infection cases (regardless of symptoms) during the EAP is defined as time to first RT-PCR-confirmed SARS-CoV-2 infection cases (regardless of symptoms) during the EAP. Similar rules to primary efficacy variable are applied to this variable.
3. Proportion of participants with COVID-19-related hospitalization, emergency room visit, urgent care center visit or death during the EAP and follow-up period is defined as number of participants with COVID-19-related hospitalization, emergency room visit, urgent care center visit or death during the EAP and follow-up period divided by total number of participants of interest.
4. Maximum SARS-CoV-2 RT-qPCR viral load (\log_{10} copies/mL) in NP swab samples among individuals with ≥ 1 RT-qPCR positive test that has an onset during the EAP is defined as the maximum value of viral load (\log_{10} copies/mL) among all the NP swab samples from individuals with ≥ 1 RT-qPCR positive test that has an onset during the EAP.
5. Viral variant characteristics of SARS-CoV-2 in participants who become infected post-baseline

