### Optional Dose

The Sponsor believes that casirivimab+imdevimab may continue to serve as an important pre-exposure prophylaxis therapeutic among immunocompromised individuals in regions where Omicron is not the dominant variant or in regions where Omicron prevalence subsides. For this reason, participants will have the option to receive a 1200 mg SC dose of casirivimab+imdevimab as a final study dose. This optional dose may be administered to all participants regardless of treatment assignment at randomization. However, participants will not be eligible to receive this dose if they have already received casirivimab+imdevimab as post-infection treatment.

Participants will be asked to return to the site for an unscheduled visit, during which they will be asked to consent to protocol amendment 2 and receive the final optional dose, if desired. This visit to receive the final optional dose should occur approximately 4 weeks after the most recent dose. Note that consent may be obtained remotely prior to this visit, if available and allowable by the study site.

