**Table 1: Schedule of Events (No Longer Applicable as of Protocol Amendment 2)**

Study Day	Screening/Baseline 				Efficacy Assessment Period 					Follow-Up Period 			Confirmatory Visit, Suspected COVID-19 	Post-Infection Treatment Visit, Lab-Confirmed Infection 	ET			
	-14 to 1		1		8 	29	57	85	113	141	169	197 (FU 1)	225 (FU 2)	253 (EOS)				
	Screen	Pre-Dose	Dose	Post-Dose														
Window (Day)					±3	±7	±7	±7	±7	±7	±7	±7	±14	±14	±14			
Screening/Baseline																		
Informed consent	X																	
Inclusion/exclusion	X																	
Medical history	X																	
Demographics	X																	
Weight and height	X																	
Locally-acceptable sample for SARS-CoV-2 RT-PCR (local) 	X																	
NP swab sample for SARS-CoV-2 RT-qPCR (central) 		X																
Randomization		X																
Treatment																		
Study drug administration 			X		X	X	X	X	X									
Safety																		
Vital signs 		X		X		X	X	X	X	X	X							
Treatment-emergent grade ≥3 AEs 			X	X	X	X	X	X	X	X	X	X	X			X		
Treatment-emergent AEs leading to study drug discontinuation 			X	X	X	X	X	X	X	X	X	X	X			X		
Treatment-emergent SAEs 			X	X	X	X	X	X	X	X	X	X	X			X		
Treatment-emergent grade ≥2 hypersensitivity reactions 			X	X	X	X	X	X	X							X		
Treatment-emergent grade ≥3 ISRs 			X	X	X	X	X	X	X							X		
Concomitant medications and procedures	X			X	X	X	X	X	X	X	X	X	X			X		
Pregnancy test, blood or urine (WOCBP only)	X				X		X		X									
Pregnancy status											X		X			X		
Vital status				X							X	X	X			X		
Safety information (newborns of study participants)													X			X		
Efficacy																		
Clinician assessment of COVID-19 signs and symptoms			X		X	X	X	X	X	X	X	X	X			X 		
Central Laboratory Pharmacodynamic/Biomarker Testing																		
Serum for central anti-SARS-CoV-2 serological assays		X 																
Serum for exploratory research		X 									X							
Plasma for exploratory research		X 								X								

Study Day	Screening/Baseline 				Efficacy Assessment Period 					Follow-Up Period 			Confirmatory Visit, Suspected COVID-19 	Post-Infection Treatment Visit, Lab-Confirmed Infection 	ET			

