Post-Infection Treatment. Participants with confirmed positive SARS-CoV-2 RT-PCR will be eligible for post-infection treatment (as described in protocol Section 6.4.4) at any time prior to receipt of the optional 1200mg SC dose (eg, during the 4 weeks between receipt of the last protocol-defined dose and optional 1200 mg SC dose). Once this optional dose has been

administered, post-infection treatment will no longer be offered. Likewise, any participant who receives post-infection treatment will not be eligible to receive the optional 1200 mg SC dose.

Participants with Positive SARS-COV-2 RT-PCR. Participants with a positive SARS-CoV-2 RT-PCR may have additional assessments and sample collections, including unscheduled visits every 7

days (± 1 day) for central laboratory RT-qPCR analysis until 2 consecutive negative test results are obtained:

- NP swab samples for RT-qPCR
- COVID-19 signs and symptoms evaluated by the investigator or designee
- Information regarding COVID-19-related medically-attended visits (MAVs; defined in protocol Section 9.2.4.3)

End-of-Study Visit

All participants, including those who do not consent to receive the optional final dose, will have a follow-up (end-of-study) telephone visit approximately 85 days (3 months) from their last dose of investigational drug (casirivimab+imdevimab or placebo) to monitor safety. Study assessments for the 3-month follow-up visit will be limited to the collection of targeted adverse events, as detailed in the new schedule of events (protocol amendment 2 Table 2).

Sites will ensure that an additional discussion about the potential risks and benefits to the participant and fetus is discussed as part of re-consent for participants who become pregnant during the study.

Analysis Plan

At the time that enrollment was closed, 66 participants had been enrolled in the study. Due to the early study closure and the resulting small sample size of enrolled participants, all analyses will be performed descriptively and only numeric comparisons will be performed. All safety endpoints (including AEs, TEAEs, AESIs, SAEs, and safety laboratory values) will be summarized. Selected efficacy, virology, PK, and/or immunogenicity data may also be analyzed descriptively. No interim analysis will be performed for this study, and no IDMC review meetings will occur.

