4.6.3. Vital Signs and Laboratory Tests

Standard vital signs including body temperature, blood pressure, and heart rate, comprehensive vital sign assessment including additionally include SpO₂ and respiratory rate will be collected. Temperature and SpO₂ will be collected. Local safety laboratory tests collect absolute neutrophil count, platelet count, hemoglobin, ALT, AST, total bilirubin, and creatinine at baseline visit as well as study visits days 29,85 and 169.

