5.6.2. Exposure to Investigational Product

The duration of study treatment exposure will be defined as day 1 through 4 weeks, ie, 28 days, after the last dose for a participant in the Q4W arms and day 1 through 12 weeks, ie, 84 days after the last dose for a participant in the Q12W arm. The duration of the study will be through the follow-up period defined as end of EAP through day 253 (± 14 days). Treatment exposure and study duration will be evaluated in the SAF.

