5.8. Analysis of Safety Data

Secondary safety endpoints are

1. Proportion of participants with grade ≥ 3 treatment-emergent adverse events (TEAEs), during the EAP and follow-up period
2. Proportion of participants with TEAEs leading to study drug discontinuation, during the EAP and follow-up period
3. Proportion of participants with treatment-emergent serious adverse events (SAEs) during the EAP and follow-up period
4. Proportion of participants with adverse events of special interest (AESIs) during the EAP

For safety variables, the following observation periods are defined:

- The pretreatment period is defined as the time from the signing of the ICF to before study drug administration.
- The EAP is defined as the day from first dose of study drug to day 169 ± 7 days
- The Follow-up period is defined as the end of the EAP to the end of the Follow-up Period (ie, the last study visit).

The safety analysis will be based on the reported AEs and other safety information (clinical laboratory evaluations, and vital signs). The summary of AE results will be presented for each treatment group for each of three TEAE periods: treatment-emergent EAP (TEEAP), treatment-emergent follow-up period (TEFUP), and overall study period (i.e., combined across the TEEAP and TEFUP). For laboratory and vital sign results they will be presented for each treatment group for each of three periods: EAP, follow-up, and overall study period.

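### The SAP's follow-up analyses were not re-anchored to the Amendment 2 close-out schedule, so who is observed in follow-up, and over what denominator, is left undefined

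*SAP*

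**What the plan says.** The SAP, signed in June 2022, postdates Amendment 2. Its appendix marks the schedule with visits at days 197, 225 and 253 as no longer applicable and reproduces the close-out schedule for all enrolled participants. Under that schedule:

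- Optional dose (Protocol, Optional Dose): "This visit to receive the final optional dose should occur approximately 4 weeks after the most recent dose". The window is ±7 days.
- Last contact (SAP 1.1): a "telephone visit approximately 85 days (3 months) from their last dose of investigational drug". The window is ±14 days, and the call is limited to targeted adverse events.
- COVID-19 assessments (Protocol 9.1.2, footnote 6): optional for both site and participant.

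The SAP nevertheless retains:

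- Follow-up incidence (4.5.2 item 1, repeated in 5.7.3): "Cumulative incidence of symptomatic (broad term), RT-PCR-confirmed SARS-CoV-2 infection cases during the follow-up period is defined as time to first symptomatic infection", under rules similar to those for the primary variable.
- One of those rules (4.5.1): "If subjects took optional dose of 1200mg, all the data after the dose will be removed from the efficacy analyses".
- Adverse event summaries (5.8) for "treatment-emergent EAP (TEEAP), treatment-emergent follow-up period (TEFUP), and overall study period", with laboratory and vital-sign results also shown separately for follow-up.
- Laboratory sampling (4.6.3): "creatinine at baseline visit as well as study visits days 29,85 and 169".
- Study duration (5.6.2): "The duration of the study will be through the follow-up period defined as end of EAP through day 253".

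SAP 3.2 assigns all clinical safety variables to the safety analysis set, meaning everyone who received any study drug. SAP 5.8.1 asks for numbers and percentages by treatment group. Neither gives a denominator specific to the follow-up period.

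**The concern.** The end of the efficacy assessment period (EAP) is a fixed study day, while the end of observation now depends on each participant's last dose. A participant who stopped assigned dosing early can finish the study well before day 176 and never enter the period that the follow-up tables describe.

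Two outputs could mislead. Follow-up incidence could rest on a small, self-selected group: people who declined the optional dose and had already received most of their assigned doses. A follow-up adverse event table could print 0/16 (0%) for an arm in which few people were still in contact, and a reader would take that as evidence of no late events. The follow-up laboratory table would have no scheduled data behind it.

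**Working it through.** **The plan's own figures.** The EAP case window ends at 169 + 7 = day 176 (SAP 5.7.1). The superseded follow-up ran 253 − 169 = 84 days, the planned three months. Days 177 to 253 inclusive are 77 days. 66/4 = 16.5 per arm, matching the 16 to 17 in SAP 2.1.

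**Nominal last contact.** Assigned dosing days D are 1, 29, 57, 85, 113 and 141. All arms are injected every 4 weeks, with placebo filling in, so the same days apply to the Q12W arm. If the optional dose is declined, the call is on D + 85. If it is taken, the dose is on D + 28 and the call on D + 28 + 85 = D + 113.

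| Assigned doses | D | Call, declined | Days past 176 | Optional dose | Call, taken | Days past 176 (safety only) |
|---|---|---|---|---|---|---|
| 1 | 1 | 86 | 0 | 29 | 114 | 0 |
| 2 | 29 | 114 | 0 | 57 | 142 | 0 |
| 3 | 57 | 142 | 0 | 85 | 170 | 0 |
| 4 | 85 | 170 | 0 | 113 | 198 | 22 |
| 5 | 113 | 198 | 22 | 141 | 226 | 50 |
| 6 | 141 | 226 | 50 | 169 | 254 | 78 |

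**Efficacy time after day 176.** For takers, efficacy data stop at the optional dose, nominally day 169 at the latest, so follow-up efficacy time is zero. Stacking both windows (141 + 7 = 148, then 148 + 28 + 7 = 183) allows at most 183 − 176 = 7 days. For decliners it is 22 or 50 days after five or six doses. With four doses it is possible only at the window edge: 85 + 85 + 14 = day 184.

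**How many participants.** The documents give neither the first enrolment date, nor the date assigned dosing stopped, nor the optional-dose uptake. As an illustration, assume uniform accrual up to 16 December 2021 (when enrolment closed) and assigned dosing every 4 weeks up to a date T. Two assumed start dates are used: 10 September 2021 (an access date in the protocol's reference list) and 21 October 2021 (the site memorandum). The entries are the approximate number of 66 nominally in contact past day 176.

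| Start | Optional dose | T = 16 Dec | 15 Jan | 15 Feb | 15 Mar |
|---|---|---|---|---|---|
| 10 Sep | all decline | 0 | 11 | 32 | 50 |
| 10 Sep | all take (safety only) | 9 | 30 | 50 | 66 |
| 21 Oct | all decline | 0 | 0 | 7 | 39 |
| 21 Oct | all take (safety only) | 0 | 4 | 39 | 66 |

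If everyone took the optional dose, the nominal number at risk for follow-up incidence is 0 in every scenario.

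**Denominator effect.** One follow-up event in an arm is 1/16.5 = 6.1% on the safety set. If only 8 were observed after day 176 it would be 1/8 = 12.5%, and if only 4, 1/4 = 25%. The counts 8 and 4 are illustrative.

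**Expected cases.** Take λ = −ln(1 − 0.0402) per 6 months (182.5 days), the hazard ratios 0.40, 0.45, 0.55 and 1 implied by Protocol Table 6, and 16.5 per arm fully observed for 77 days. Then 16.5 × [1 − exp(−λ × HR × 77/182.5)] gives 0.114 + 0.128 + 0.156 + 0.283 ≈ 0.68 cases in total.

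**Censoring.** SAP 4.5.1 censors participants without infection at their last observed time point, but censors those who die or discontinue early at the end of study. Carried over to follow-up incidence, the second rule places early discontinuers at risk during time when nobody observed them.

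**The case against.** The strongest reply is that little turns on this. SAP section 1 designates every endpoint exploratory, SAP 1.1 makes all analyses descriptive, and SAP 1.2.4 already allows exploratory endpoints to go unreported. Even with complete observation, fewer than one follow-up case would be expected at the protocol's rates. The overall-period safety summary is already planned. Protocol 3.3.2 also wants participants followed through drug elimination, which is a reason to keep some follow-up reporting. All of this stands, and it limits the importance of the point.

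Some stronger readings are tempting, and the documents do not support them:

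- A reader might infer that Amendment 2 abolished follow-up. It replaced the visit schedule. A follow-up telephone visit remains, and the safety definition runs to the last study visit, not to a fixed day 253.
- A reader might infer that almost nobody is at risk. That holds nominally for optional-dose takers. For decliners the scenarios run from 0 to about 50 of 66. An entrant on 16 December 2021 reaches the fifth dose only on 7 April 2022, but an entrant on 10 September 2021 would reach it on 31 December 2021.
- A reader might infer that follow-up always begins after day 176. SAP 4.4.2 moves RT-PCR-positive participants into follow-up at once.
- A reader might infer that the SAP expressly counts unobserved participants as event-free. It does not say so. The conclusion follows from the all-treated safety set together with silence on a period denominator.
- A reader might infer that vital signs cannot exist after day 176. A late optional-dose visit can supply them, as can an optional suspected-COVID-19 visit, and SAP 6.4 lets unscheduled measurements be used. For laboratory tests the gap is firmer: nothing is scheduled after day 169.

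**Conclusion.** The point holds as a gap in definition. The SAP adopts a schedule tied to the last dose but keeps follow-up analyses designed for fixed visits, and does not say who is observed in follow-up or what the percentages are taken over.

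Follow-up incidence has nominally zero efficacy time for takers (seven days at most with every visit in window) and at most 50 nominal days for decliners, against 77 planned, with case ascertainment optional. The follow-up adverse event percentages, read with SAP 3.2, would include people whose contact ended before the period began. The effect is on how the results read, not on any test.

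The day arithmetic assumes dosing and calls on their nominal days, except where windows are stated. The participant counts rest on assumed accrual and dosing dates and show a range only.

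**What to change.** Four changes to the SAP:

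1. **5.8.** Take as the follow-up adverse event denominator the participants observed in that period, and print person-days beside it. State how participants who enter follow-up early after a positive RT-PCR are counted. Alternatively, present only the overall period, which is already planned.
2. **5.6.2.** Define study duration as last contact date − first dose date + 1, in place of the day 253 endpoint.
3. **5.8 and 5.8.3.** Drop the follow-up laboratory table. List any vital signs taken after day 176 instead of tabulating them.
4. **4.5.2 item 1 and 5.7.3.** Either drop follow-up incidence and record this in 1.2.4, or keep it with the number at risk shown and censoring at the optional dose or last efficacy contact, not at the end of study.

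The primary endpoint should keep its day 2 to day 176 limit. Extending it to the last efficacy contact would change its definition.

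The cost is wording and denominators, with no new data. At most one exploratory endpoint is lost, or it is reported with few participants.
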